For each outcome event and for each study cohort, the number of first events, total person-years for the event, number of first events per person-years (rate), the rate ratio (RR) and the VE, calculated as (1 - RR)) will be presented. This will also be provided per age group and per frailty score. Finally, VE will also be provided in shorter periods after dose 1, and between the doses, and by presence of comorbidities. Poisson regression will be used to estimate rates using the matched dataset, adjusting for the matching variables and body mass index (BMI), smoking, prescribed medications, and frailty score.

RAVEN extension analyses (other than VE):

- a) Populations at risk: Exploratory analysis of populations at risk of breakthrough COVID-19 and populations with a contraindication to vaccination will be carried out with the aim to better describe these populations at risk of COVID in a highly vaccinated population (e.g. to identify populations, and estimate their size). Artificial intelligence/machine learning (AI/ML) methods will be employed to predict breakthrough cases, time to vaccine waning and predictors of accepting booster doses.
- b) HCRU and health care cost related to COVID-19: The non-linear trends over time in healthcare service use and costs will be explored using inverse probability weighted generalized estimating equations (GEE). Estimates of the incremental health service use and incremental health service costs associated with receipt of COVID-19 vaccine will be over 1, 3 and 6 months of follow-up.
- c) Household incidence/transmission: Vaccinated and non-vaccinated cases with a positive SARS-CoV-2 test will be identified (index cases), along with their household contacts. The proportion of unvaccinated and vaccinated contacts who test positive for SARS-CoV-2 after the index case (secondary cases) will be compared among the vaccinated and non-vaccinated index cases. Logistic regression will be used to estimate the odds (and 95% confidence intervals (CI)) of being a secondary case, adjusting for confounders.
- d) Long COVID: Cases of long COVID will be described, including by initial COVID-19 disease severity. The impact of vaccination on the occurrence of long COVID (in vaccinated individuals, in vaccinated individuals with COVID-19) will be explored.

Milestones

Expected data collection:	
Interim reports:	
Final report:	

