9.2.2 Inclusion Criteria

The study population is required to meet the following inclusion criteria:

1. For the vaccinated arms:

- Any COVID-19 vaccination at the index date
- Have continuous data coverage for the COVID-19 infection datasets, i.e. Second Generation Surveillance System (SGSS) and National Pathology Exchange (NPEX) from their initiation for history of prior COVID-19 infection
- Have continuous data coverage in other linked databases for a minimum of 12 months prior to the index date for assessment of baseline variables including socio-economic status, comorbidities, and follow-up of outcome events.

2. For the control arms:

- Eligible for any COVID-19 vaccination based on age at the index date for the concurrent control individuals.
- Have continuous data coverage for the COVID-19 infection datasets, i.e. SGSS and NPEX from their initiation for history of prior COVID-19 infection
- Have continuous data coverage in other linked databases for a minimum of 12 months prior to the index date for assessment of baseline variables including socio-economic status, comorbidities, and follow-up of outcome events.
- People who have not (yet) received any COVID-19 vaccine (Oxford/AstraZeneca, Pfizer, or Moderna COVID-19 vaccine) recorded in their GP record or in NIMS. They will be used as concurrent controls. However, they will be censored at date of vaccination and, then may re-enter the study as newly vaccinated individuals.

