9.2.3 Exclusion Criteria

People who meet the following criteria will be excluded:

• Primary analysis: People with a history of COVID-19 infection (confirmed by reverse transcriptase polymerase chain reaction (RT-PCR) or not) prior to vaccination. This group of people is not excluded in the sensitivity analysis.

A sensitivity analysis excluding persons living in an elderly care home will be considered.

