9.3.3 Other Variables and Covariates

Table 6. Variable categories and data sources

Variables	Categories	Data source	Comment
Age	Different categorizations may be used -12 <50; 50-<65; 65-<70; 70-<80; 80+ -18-<40; 40-<50; 50+; 65+; 70+; 80+	GDPPR	BMI is binary as obese or not using HES, SUS, GDPPR or BMI can be created from weight/height if
Gender	Male/Female	-	available;
Ethnicity	White, Black, Asian, Other, Mixed		
Region	NHS Region	-	
Sociodemographic	Socioeconomic status – Index of Multiple Deprivation (IMD)		
BMI	-Obese (BMI 30+) -Not-obese (BMI <30)		
Smoking	- Current - Past - Non smoker		
Comorbidity	Specific comorbidities known to relate with increased risk of severe COVID- 19 and/or suboptimal vaccine response and/or vaccine contraindication including chronic respiratory disease, chronic kidney disease, chronic heart disease and vascular disease, chronic liver disease, chronic neurological disease, diabetes mellitus, severe mental illness, morbid obesity, asplenia or dysfunction of the spleen, and immunosuppression due to disease or treatment.	ORCIHD, HES and GDPPR	Follow JCVI/Green book list of comorbidities (COVID-19 Greenbook chapter 14a) Using ICD or SNOMED codes to identify comorbidities during the baseline period. For immunosuppressant medications, see Prescribed medication section below.
CMMS	0, and by quartile		Created from specific comorbidities;
Non-COVID-19 vaccination	 Flu vaccination (Y/N) Receive adequate vaccination (Y/N) 	GDPPR	An algorithm will be developed to determine if an individual is adequately vaccinated according to recommended vaccination schedule by age and comorbidity status
Prescription medication	Immunosuppressant vs. not	GDPPR	Prescribed medications at baseline will be grouped into immunosuppressant or not.
LTC /assisted living care facility	Yes/No	Not in any database	To be created for people aged 70+ by comparing their zip codes and LTC

Variables	Categories	Data	Comment
		source	
			address; or vaccination at LTC facility. (ORCHID)
Household composition	Size and age combination.	ORCHID UKHSA VE cohort	Available for 7.2 million subset of ORCHID
Frailty score	eFI grouped into - Mild - Moderate - Severe	Derived from GDPPR	Use an algorithm already developed to derive eFI, only available for population 65years and older. For this sub-group analysis.

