9.7.5 Feasibility Assessment for Further Exploratory Analyses

To understand the VE on different variants of the coronavirus, we will describe the VE by a combination of region and time period that aligns with best knowledge of when and where new variants of the virus were present according to available data sources and explore mechanisms for future individual level studies.

To study the VE among people in long term care (LTC) or assisted living facilities in the subset of subjects with data available on household key, median household age (>60), and number of residents (9 or more) and can be linked to the Care Quality Commission register, which lists residences where a degree of nursing care is provided. These variables will be used as a proxy to identify individuals receiving LTC at home or at specialized facilities.

9.7.6 **RAVEN Extension Analyses (Other than VE)**

9.7.6.1 **Populations at Risk and Predictors of Having Boosters**

The risk profile of the population at risk of COVID-19 due to either being ineligible for COVID-19 vaccines or due to suboptimal vaccine response (i.e. immunocompromised individuals) will be described. Specific subgroups (including their size) may be identified. AI/ML methods will be applied to explore the risk profile of the population at risk of COVID due to suboptimal vaccine response, and thus who may be more likely to experience breakthrough cases. A breakthrough case is defined as a person who has a positive virology test for the COVID-19 virus 14 or more days after their second vaccination (CDC definition (CDC, 2021)). We will consider predictions of breakthrough cases of SARS-CoV2 infections and clinically significant breakthrough infections (i.e. the primary outcomes), the identification of susceptible sub-populations and predictions of the time to vaccine waning with respect to these outcomes. People who are immunocompromised are the primary population of interest. AI/ML methods will also be used to identify predictors of receiving AZ boosters.

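### Controls qualify on age and an absent vaccination record alone, so people with a recorded contraindication can be controls although the protocol plans to identify them as ineligible; the bias is of unknown size

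*Protocol*

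**What the plan says.** **Who can be a control.** Protocol 9.2.2 asks that controls be "Eligible for any COVID-19 vaccination based on age at the index date for the concurrent control individuals", have the required data coverage, and have no COVID-19 vaccine "recorded in their GP record or in NIMS. They will be used as concurrent controls". Eligibility is judged on age; there is no clinical condition.

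**Who is excluded.** Section 9.2.3 lists one exclusion for the primary analysis: "People with a history of COVID-19 infection (confirmed by reverse transcriptase polymerase chain reaction (RT-PCR) or not) prior to vaccination". The care-home exclusion is a sensitivity analysis only (9.2.3, 9.7.3).

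**Matching and adjustment.** Section 9.7.1 matches weekly, 1:1, from 8 December 2020 on age band, gender, practice or NHS region, and quartile of the Cambridge Multimorbidity Score (CMMS). The Poisson model adds BMI, smoking, prescribed medications and frailty. Contraindication appears in neither list, nor among the sensitivity analyses in 9.7.3.

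**Follow-up.** Under 9.2.4 a control is censored at vaccination, and a vaccinee when the matched control is vaccinated.

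**Where the protocol recognises the group.** The Synopsis says that exploratory analysis of "populations with a contraindication to vaccination will be carried out with the aim to better describe these populations", including an estimate of their size. Section 8 repeats the aim for people who are ineligible for vaccination. Section 9.7.6.1 will describe people at risk "due to either being ineligible for COVID-19 vaccines or due to suboptimal vaccine response". Table 6 (9.3.3) collects comorbidities related to severe disease, "suboptimal vaccine response and/or vaccine contraindication".

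**The concern.** The same people are treated as ineligible for vaccination in one analysis and as eligible comparators in the main one. A vaccinee had some chance of being vaccinated; a person with a standing contraindication has little or none for as long as it lasts. Two features of the design concentrate such people among the controls:

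- As coverage rises, others leave the unvaccinated pool and these people stay.
- Follow-up of a pair ends when its control is vaccinated, so pairs whose control stays unvaccinated contribute more person-time. This weighs most on the later time bands, and time since dose is part of the primary objective.

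If these people have a higher event rate than other controls with the same matching and adjustment values, the control rate is too high and VE is overstated. If their rate is lower, the bias reverses. The economic analysis in 9.7.6.2 mirrors the comparator groups and inherits the problem. Section 9.1 names two kinds of atypical remaining control, people in terminal care and people who engage little with the health system, but not this one.

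**Working it through.** The protocol states no figure for this bias, so there is none to reproduce.

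**Inputs from the protocol (9.5, as of 7 April 2021).** Coverage v is 42.1% overall, 79% in risk groups aged 16 to 64, and 91% at ages 65 to 79 and at 80 and over.

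**Assumed, because the protocol gives no values.** Prevalence of contraindication c = 0.05% to 1%; residual rate ratio k = 2 between contraindicated and other controls after matching and adjustment; true VE = 80% (rate ratio 0.2); weekly vaccination hazard h = 0.02 to 0.10 over 26 weeks.

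**Step 1: share of the unvaccinated pool.** If contraindicated people stay unvaccinated, s = c/(1 − v). The enrichment 1/(1 − v) is 1/0.579 = 1.73 at 42.1%, 1/0.21 = 4.76 at 79%, and 1/0.09 = 11.1 at 91%.

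**Step 2: bias if all matching happened at 91% coverage.** The control rate is multiplied by F = 1 + s(k − 1). Observed VE = 1 − 0.2/F; a vaccine with no effect shows 1 − 1/F. With k = 2:

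| c | s = c/0.09 | F | true 80% reads | null reads |
|---|---|---|---|---|
| 0.05% | 0.56% | 1.0056 | 80.1% | 0.6% |
| 0.1% | 1.11% | 1.0111 | 80.2% | 1.1% |
| 0.5% | 5.56% | 1.0556 | 81.1% | 5.3% |
| 1% | 11.1% | 1.1111 | 82.0% | 10.0% |

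**Step 3: matching spread over uptake.** Matching is weekly, so most vaccinees are matched before coverage reaches its final level. If enrolment runs evenly from 0 to 91%, the mean share at matching is (c/0.91) × ln(1/0.09) = c × 2.408/0.91 = 2.65c. At c = 1% and k = 2, F = 1.0265. A true 80% then reads 1 − 0.2/1.0265 = 80.5%, and a null reads 1 − 1/1.0265 = 2.6%.

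**Step 4: person-time weighting.** Other controls contribute on average m = (1 − e^(−26h))/h weeks, contraindicated controls 26 weeks. The ratio a = 26/m is 1.28, 1.79 and 2.81 at h = 0.02, 0.05 and 0.10. The person-time share is w = s·a/(s·a + 1 − s). With s = 2.65%:

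- a = 1.28: w = 0.0339/(0.0339 + 0.9735) = 3.4%; a true 80% reads 1 − 0.2/1.034 = 80.7%.
- a = 2.81: w = 0.0745/(0.0745 + 0.9735) = 7.1%; a true 80% reads 1 − 0.2/1.071 = 81.3%.

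Applying the same weights to s = 11.1% gives 82.4% to 84.1%. That stacks the highest assumed prevalence, matching entirely at final coverage and continued vaccination of the other controls, so it is an outer bound.

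**The case against.** **Size and direction are assumed.** This stands. The protocol gives no prevalence and no excess risk. At 0.1% or below, a true 80% moves by about 0.2 points even at 91% coverage, and the sign depends on k being above 1.

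**A reader might take the 91% pool as the condition under which people are matched.** The protocol does not support that. Matching is weekly from December 2020, and under even uptake the mean enrichment is 2.65-fold, not 11.1-fold. Null readings of 10% at k = 2, or 18% at k = 3, both with c = 1%, belong to that extreme.

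**A reader might infer that these people could never be vaccinated.** The protocol does not say that a contraindication is permanent or covers every product. Several vaccines are in use, and a control who is later vaccinated is censored and may re-enter as vaccinated.

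**A reader might conclude that VE is undefined with such controls.** The design matches controls to vaccinees and so estimates an effect among the vaccinated. These controls bias it only if contraindication predicts the outcome beyond the matched and adjusted variables. CMMS quartile, medications and frailty will absorb some of that difference.

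**A reader might expect the bias to be worst in the immunocompromised subgroup.** Section 9.7.6.1 places immunocompromised people under suboptimal response, not contraindication, so this is unsupported.

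**Identification is planned, not shown to be feasible.** The protocol contains no contraindication code list; the ENCePP checklist (Appendix B) defers code lists to the SAP. Table 6 combines contraindication with conditions such as diabetes and respiratory disease, so excluding on it would remove groups that the primary objective must study. Section 9.4 notes that GDPPR holds a restricted set of clinical codes.

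**The plan recognises atypical controls in general.** Section 9.1 does, and 9.7.1 will refine matching if important differences appear. Contraindication is not named as a characteristic to check, so this does not settle the point.

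**Conclusion.** The point holds as an inconsistency in the eligibility criteria with a cheap remedy. It is not a demonstrated large bias. Control eligibility rests on age, data coverage and absence of a recorded dose; nothing removes, matches on or adjusts for contraindication; and the protocol elsewhere undertakes to identify and size this population. Eligibility is fixed in the protocol, so this is not a detail left to the SAP.

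On the assumed prevalence of 0.05% to 1% and twice the residual risk, the likely overstatement of a true 80% VE runs from negligible to about one point when matching is spread over uptake, and reaches two points if all matching happened at 91% coverage. It is larger where the true effect is weaker, which may apply to the all-cause secondary outcomes. These results assume that contraindicated people stay unvaccinated, and the direction assumes that they are at higher risk after adjustment.

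**What to change.** Add to 9.2.3, for the VE analyses and for the cost analyses in 9.7.6.2 that mirror them: exclude from both arms people with a specific recorded contraindication to COVID-19 vaccination on or before the index date. Use only information recorded by that date.

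Use the contraindication-specific code list that must be built for 9.7.6.1, not the general comorbidity list in Table 6. Keep these people in the descriptive population-at-risk analysis, and report how many the exclusion removes from each arm.

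If the coding proves too incomplete in GDPPR, add the exclusion to 9.7.3 as a sensitivity analysis where it can be coded, for example in ORCHID, and state the limitation in 9.9.

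The cost is one protocol line, reuse of a code list already needed, and a small loss of controls. Unrecorded contraindications will remain.

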9.2.3 Exclusion Criteria

People who meet the following criteria will be excluded:

• Primary analysis: People with a history of COVID-19 infection (confirmed by reverse transcriptase polymerase chain reaction (RT-PCR) or not) prior to vaccination. This group of people is not excluded in the sensitivity analysis.

A sensitivity analysis excluding persons living in an elderly care home will be considered.

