9.2 Setting

9.2.1 Study Population

The study population of this study is people in England who have received at least one dose of the Oxford/AstraZeneca COVID-19 vaccine from January 2021 onwards (the AstraZeneca vaccine arm) or at least one dose of another (e.g. mRNA) COVID-19 vaccine from December 2020 onwards (the Other vaccine arm) and people in England who were not vaccinated with any COVID-19 vaccine during the same time period (concurrent control arm) who will be matched to the vaccinated individuals by age, gender, GP practice (NHS region), and comorbidity (see Section

9.7.1 for a description of matching). Study participants of any age will be considered. For the vaccinated individuals, the study's index date is the date of vaccination of the 1st dose.

Concurrent controls who become vaccinated will be censored at date of vaccination and, then may re-enter the study as newly vaccinated individuals. An appropriate control group will be identified for the booster dose evaluation.

To contextualize, we will describe the impact of SARS-CoV2 on the unvaccinated English population, prior to the availability of COVID-19 vaccines. We will conduct a descriptive analysis of COVID-19 of this historical population of unvaccinated persons in England.

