9.3.2 Outcomes

The primary outcomes of this study are

- COVID-19 related hospitalization
- COVID-19 related ICU admission
- COVID-19 related death

The secondary outcomes of this study are

- All-cause hospitalization
- All-cause ICU admission
- All-cause mortality

The RAVEN extension outcomes are:

- Any positive SARS-CoV-2 test
- Medically attended COVID-19
- Emergency department visit associated with COVID-19
- HCRU (including but not limited, primary care consultations, prescriptions, medical tests and investigations; hospital outpatient attendances and procedures; hospital emergency department attendances without admission; hospital admissions) and associated cost related to COVID-19 and long COVID
- Breakthrough case
- Time to vaccine waning
- Long COVID (e.g. based on code for long COVID, on combination of code for long COVID and a positive SARS-CoV-2 test, on referral to long COVID clinic)
- A COVID-19 related event (GP attendance, accident department, hospitalization, ICU admission, death) is defined as:

- A medically attended event "Acute symptomatic COVID" defined as a positive test plus a clinical diagnosis or symptom (e.g. anosmia) which makes COVID plausible
- An emergency department attendance
- An event with an ICD-10 diagnosis of COVID-19
- An event within 28 days of a positive RT-PCR for SARS-CoV-2 infection or
- A visit with a patient presenting with respiratory symptoms or other symptoms credibly associated with COVID-19 within 28 days of a positive RT-PCR for SARS-CoV-2 infection.
 - Events within 14 days will feature in a sensitivity analysis.

Events of interest are those occurring between the index date and the end of follow-up. Only the first outcome event will be considered in the primary and secondary VE analysis.

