9.7.3 Sensitivity Analyses

Several sensitivity analyses will be considered

- Only HES data are included for follow-up data on hospitalization and ICU-admission
- People with history of COVID-19 infection prior to vaccination not excluded from the study population
- A COVID-related event within 14 days of a positive RT-PCR for SARS-CoV-2 infection.
- Addition of the following exclusion criterion: People whose household had more than 10 people with an average age of 65 years and over. This is a proxy for people living in an elderly care home (and only available for a subset of ORCHID data). They will generate a strong confounding effect of (due to the targeted vaccination of these residents and their high risks of COVID-19-related events) and the lack of available controls.

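### The prior-infection exclusion is tied to vaccination, an event controls do not have at time zero; it should be tied to the index date in both arms

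*Protocol*

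**What the plan says.** Section 9.2.3 contains the only prior-infection exclusion. For the primary analysis it removes "People with a history of COVID-19 infection (confirmed by reverse transcriptase polymerase chain reaction (RT-PCR) or not) prior to vaccination". Section 9.7.3 lifts the exclusion in a sensitivity analysis and keeps the anchor: "People with history of COVID-19 infection prior to vaccination not excluded from the study population".

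The index date is defined in 9.2.1 for one arm: "For the vaccinated individuals, the study's index date is the date of vaccination of the 1st dose". Section 9.2.2 mentions an index date for concurrent controls when it sets age eligibility, but neither that section nor any other says what the date is. Sections 9.2.4 and 9.3.2 nevertheless start follow-up and outcome counting from it in both arms ("Events of interest are those occurring between the index date and the end of follow-up").

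Controls are described in 9.2.2 as "People who have not (yet) received any COVID-19 vaccine (Oxford/AstraZeneca, Pfizer, or Moderna COVID-19 vaccine) recorded in their GP record or in NIMS". If vaccinated later, "they will be censored at date of vaccination and, then may re-enter the study as newly vaccinated individuals". Controls must also meet a data-coverage condition: "Have continuous data coverage for the COVID-19 infection datasets, i.e. SGSS and NPEX from their initiation for history of prior COVID-19 infection".

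The matching variables in 9.7.1 are age, gender, practice or region, and comorbidity. The Poisson model adds BMI, smoking, prescribed medications and frailty score. Prior infection is in neither list.

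**The concern.** An eligibility rule in a matched cohort has to be decidable for both members of a pair at the same moment, from information available then. This one is anchored to an event that defines one arm and is absent from the other at time zero.

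The main consequence is asymmetry. A never-vaccinated control with a past infection has no vaccination for that infection to precede, so the rule does not reach that person. A vaccinee with the same history is removed. The control arm would then carry natural immunity that has been screened out of the vaccinated arm. The control event rate falls, and so does VE.

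There is also a secondary risk in programming. The same person may be a control first and a vaccinee later, and the exclusion is worded for people, not for a period in one arm. Suppose it is coded as a single person-level flag. Someone infected after the control index date and vaccinated afterwards would meet the flag, and the control follow-up could be dropped with the rest of the record. Eligibility would then depend on what happened after time zero.

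**Working it through.** The protocol gives no event count, power figure or expected VE that depends on this rule, so there is no figure to reproduce. The check has two parts.

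**1. The stated rule applied to each type of person**

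| Person | Infected | Vaccinated | Result under 9.2.3 as worded |
|---|---|---|---|
| Vaccinee | before dose 1 | at index date | excluded |
| Control | before time zero | never | not excluded (no vaccination date) |
| Control | before time zero | later | meets the rule only through a date after time zero |
| Control | during control follow-up | later | correctly barred from re-entry as a vaccinee; the wording does not say that earlier control time is kept |

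Only the first row can be decided at time zero as written.

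**2. Illustrative size of the main effect (row 2)**

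Let λ be the event rate in unvaccinated people without prior infection, p the share of control person-time contributed by retained, previously infected controls, and q their protection against the outcome. Vaccinees with documented prior infection have been removed.

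- Control rate = λ(1 − p·q)
- Vaccinated rate = λ(1 − VE)
- VE shown = 1 − (1 − VE)/(1 − p·q)

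The inputs are assumptions: p = 5% to 20%, q = 80% to 90%.

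- Low end: p·q = 0.05 × 0.80 = 0.04, so 1 − p·q = 0.96
- High end: p·q = 0.20 × 0.90 = 0.18, so 1 − p·q = 0.82

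| True VE | VE shown, low end | VE shown, high end |
|---|---|---|
| 80% | 1 − 0.20/0.96 = 79.2% | 1 − 0.20/0.82 = 75.6% |
| 50% | 1 − 0.50/0.96 = 47.9% | 1 − 0.50/0.82 = 39.0% |

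The loss is larger in percentage points where true VE is lower. With the exclusion applied at the index date in both arms, p = 0 and the term disappears.

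**Secondary risk (row 4).** If a share f of control first events were dropped, VE shown would be 1 − (1 − VE)/(1 − f), again biased downward. The protocol offers nothing from which to set f, so no figure is given. Its reach is limited by the outcomes in 9.3.2. A control who dies of COVID-19 cannot be vaccinated later, so COVID-19 deaths cannot be lost this way. For hospitalization and ICU admission, only events survived and followed by vaccination are exposed. A positive test in itself is an extension outcome, not a primary one.

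**The case against.** The strongest reply is that the intention is clear and symmetric. Controls must have test-data coverage so that prior infection can be seen, which has little purpose unless they are screened on it. Section 9.9 describes documented prior infection as an exclusion criterion of the primary analysis without limiting it to one arm. It contrasts this with the sensitivity analysis, where the comparison drifts towards two different immune states. The amendment history (section 5) records that limitation as concerning the immunity of the unvaccinated group. With weekly 1:1 matching, a control's time zero follows naturally from the match, and the details could be left to the SAP.

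Most of this stands. It shows what was meant, and it is why the point is minor. It does not remove the defect, because the exclusion is stated in the protocol, not left open. An SAP that followed 9.2.3 to the letter would inherit the asymmetry. One that corrected it silently would differ from the protocol on who enters the primary analysis.

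A reader might go further and infer that the plan deletes control-arm events for everyone infected and then vaccinated, and that VE is badly distorted because over 90% of people aged 70 or older had a first dose by March 2021 (9.1). The documents do not support that. No section prescribes retrospective removal. Under censoring at vaccination, the natural effect of the exclusion is only to block re-entry as a vaccinee. The uptake figure describes the whole older population; it is not the share of controls who survived a COVID-19 admission and were vaccinated afterwards.

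**Conclusion.** Wrong as written, minor in severity. The exclusion in 9.2.3 and its counterpart in 9.7.3 use an anchor that controls lack at time zero, and the control's index date is left undefined. The literal rule would screen prior infection out of the vaccinated arm but not out of the never-vaccinated controls, with no correction by matching or modelling.

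The direction of the bias is downward. Its illustrated size is about 1 to 4 percentage points at a true VE of 80%, and about 2 to 11 points at 50%. These sizes rest on the assumed shares and protection, on documented prior infection being fully removed from the vaccinated arm, and on the literal reading being the one programmed. The rest of the protocol suggests that it is not the one intended. The loss of control follow-up through a person-level flag is a risk to guard against and is not an effect the plan prescribes.

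**What to change.** - **9.2.1:** add that a concurrent control's index date is the dose 1 date of the matched vaccinee.
- **9.2.3:** replace the vaccination anchor with *history of COVID-19 infection before the index date*, applied identically to both members of a pair at matching.
- **9.7.3:** use the same wording for the analysis that lifts the exclusion.
- **Re-entry:** state that when a control re-enters as a vaccinee, prior infection is re-assessed only at the new index date, and that control time and events already accrued are kept.

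The cost is about one sentence in each of these sections. No new data are needed, because the infection-data coverage required of controls in 9.2.2 already supports the check.
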